In a post-hoc analysis, the apparent role of immunogenicity in both loss of urate lowering effect and incidence of IRs was appreciated. Only 2% of subjects with anti-pegloticase antibody titers exceeding 1:2430 maintained a urate-lowering response to pegloticase compared with 63% of subjects who were treated for at least 2 months without developing high-titer antibodies ( $p < 0.001$ ) ([Sundy et al., 2011](#)). The incidence of IRs was higher among subjects who developed high-titer antibodies compared with those who had titers that did not exceed 1:2430 (60% vs. 19%;  $p < 0.001$ ) ([Sundy et al., 2011](#)). In addition, most IRs occurred when sUA levels were greater than 6 mg/dL. Retrospective analyses showed that the loss of urate-lowering efficacy, as reflected by sUA of greater than 6 mg/dL, preceded a patient's first IR, whenever it occurred, in 20 (91%) of 22 subjects treated with pegloticase every 2 weeks.

Therefore, discontinuation of pegloticase therapy in subjects who lose urate-lowering response offers a valuable approach for mitigating the risk of IR. A post-hoc analysis of the biweekly pegloticase dosing group in the randomized controlled trials (RCTs) illustrated the impact of several possible stopping rules based on sUA levels. A stopping rule based on 2 consecutive pre-infusion sUA

measurements of greater than 6 mg/dL would have significantly reduced the risk of IR (from 26% to 8%), while having little effect on the treatment response rate (from 42% to 41%) (Keenan et al., 2019). Early post-approval safety surveillance in the US using the stopping rules demonstrated a 69% reduction in the rate of IRs compared with the IR rate recorded during the RCTs (Malamet et al., 2013).

Reducing anti-drug antibodies (ADA) with concomitant administration of the immunomodulatory agent methotrexate (MTX) has been shown to be useful with other infused products that lead to immunogenicity, such as infliximab, in the setting of rheumatoid arthritis treatment. In a recent, prospective, proof-of-concept case series, nine patients with refractory tophaceous gout were pre-treated with MTX prior to co-administration of MTX with KRYSTEXXA. All nine patients were responders as defined by maintaining a serum uric acid at goal of <6 mg/dL for greater than 80% of the observation period, which ranged from 4.5 to

9 months on therapy. No unexpected adverse effects were reported with this coadministration (Botson and Peterson, 2018).

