## 9.2 Discussion of Study Design

This is a Phase 4, multi-site, open-label, single arm study to assess efficacy and safety of pegloticase in adult subjects with uncontrolled gout who have undergone kidney transplantation.

During the pre-marketing Phase 3 studies for pegloticase, subjects with organ transplant were excluded from participation; however, subjects with renal impairment were included, and showed comparable safety and efficacy as the general study population. Kidney transplant recipients with uncontrolled gout have the potential to benefit from the ability of pegloticase to rapidly deplete urate deposits, even when urate excretion is impaired. In addition, immunosuppressive agents to prevent rejections have the potential to thwart the formation of ADA against pegloticase, thereby preserving its effectiveness and decreasing the risk of infusion reactions.

This study will test safety and effectiveness of pegloticase (administered 8 mg via IV infusion every 2 weeks, consistent with the current pegloticase prescribing information) in kidney transplant subjects with chronic gout refractory to conventional urate lowering therapy.

Prospective use of sUA stopping rules, with pegloticase treatment cessation (but study continuation) when a subject has a pre-infusion sUA level >6 mg/dL on two consecutive study visits, will also help confirm the value of this approach to reduce IR risk.

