### 9.6.6 Pharmacokinetic and Anti-drug Antibody Analysis

Concentrations for pegloticase will be summarized using descriptive statistics for the PK population.

Incidence of anti-drug antibodies and titer levels will be summarized.

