### 9.6.9 Sample Size and Power Considerations

A sample size of 20 subjects is planned for this study. The primary efficacy endpoint, the proportion of subjects achieving and maintaining sUA <6 mg/dL for at least 80% of the time during Month 6, will be demonstrated to be statistically greater than 43.5% (proportion of responders during Month 6 in the Phase 3 studies), if at least 14/20 (70%) responders are observed. In that case, the lower bound of a 95% confidence interval for the proportion of responders will be about 46%.

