## **8. General Aspects for Statistical Analysis**

### **8.1. General Methods**

- In general, descriptive summaries will be provided. Efficacy summaries will show columns with “Pegloticase” as the treatment group for the ITT population. Safety summaries will be presented similarly.
- Continuous variables will be summarized using the number of observations (n), mean, standard deviation (SD), median, minimum, and maximum. Categorical variables will be summarized using number of observations (n), frequency and percentages of subjects.
- All relevant subject data will be included in listings. All subjects entered into the database will be included in subject data listings.
- The same number of decimal places as the raw data will be presented when reporting min and max, 1 more decimal place than in the raw data will be presented when reporting mean and median, and 2 more decimal places than in the raw data will be presented when reporting SD.
- Unless otherwise specified, confidence intervals (CI) will be based on 95% confidence and two-sided.
- If multiple assessments occur at a given post-baseline time point, the latest value will be used.

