## 11. Pharmacokinetics and Anti-drug Antibody Analysis

Serum samples for PK analysis of pegloticase will be collected after the end of infusion on Day 1 (prior to discharge); prior to the pegloticase infusion and after the end of the infusion (prior to discharge) at Weeks 2, 6, 14, and 22. Additional PK samples will be collected at the Week 21 Visit, the End of Pegloticase Infusions Visit (if applicable), and the Week 24/End of Study/Early Termination Visit.

Concentrations for pegloticase will be summarized using descriptive statistics by scheduled timepoint for the PK population.

The following presentations of subject serum pegloticase concentration data covered in this SAP will be provided:

- A listing including subject, week/time point (actual, planned), treatment and serum concentrations. End of infusion sampling times are expressed relative to the start time of infusion.
- A table summary of serum pegloticase concentrations at each time point (n; mean, SD, coefficient of variation (CV)% calculated as  $100\% \times SD/mean$ , minimum, 25th percentile, median, 75th percentile and maximum) for the PK Population.

Concentrations below the limit of quantification (BLQ) collected on Day 1 pre-dose will be summarized as zero. All other concentrations BLQ will be excluded from the analysis summaries.

Serum samples for evaluation of anti-PEG and anti-uricase IgG antibodies will be collected prior to the pegloticase infusion on Day 1 and at the Week 2, 6, 14, 22 Visits, the End of Pegloticase Infusions Visit (if applicable), the Week 24/End of Study/Early Termination Visit, and the 3 month Post Treatment Follow-up Visit. In the event of an AE suspected to be an infusion reaction, a serum sample will be collected in a serum separating tube at that time or at the subsequent visit for future evaluation of pegloticase antibodies.

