Using the ITT Population for anti-PEG IgG antibodies, the number and percentage of subjects with ADA positive at baseline, ADA negative at baseline, ADA positive at post-baseline but negative at baseline or with increase in titer from baseline, ADA positive at post-baseline but negative at baseline, subjects with increase in titer from baseline who were ADA positive at baseline, and ADA negative or subjects with no increase in titer from baseline will be summarized by scheduled timepoint. Similarly for anti-uricase IgG antibodies, the number and percentage of subjects with ADA positive at baseline and post-baseline will be summarized by scheduled timepoint.

Kaplan-Meier estimates of the time to positive anti-PEG, and positive anti-uricase with 25th percentile, median, 75th percentile, and 95% CI, along with a Kaplan-Meier curve will be produced. Further, the mean and coefficient of variation (CV%) of antibody titers (for samples confirmed positive) will be provided by visit and time point.

Further, the mean and CV% of pegloticase concentrations will be provided by visit in the subset of subjects who are ADA positive (defined as positive for anti-PEG or anti-uricase antibodies) and ADA negative (defined as negative for both anti-PEG and anti-uricase antibodies) for each visit. This analysis will be provided for the ITT Population.

This document is confidential.

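### Antibody titer size is to be summarized by mean and CV% in confirmed-positive samples; with few positives, one high titer can dominate, so a geometric mean titer with median and range would serve better

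*SAP*

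**What the plan says.** The protocol leaves the statistic open. Its section 9.6.6 says only: "Incidence of anti-drug antibodies and titer levels will be summarized".

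SAP 11 fills this in. For titer size it states: "Further, the mean and coefficient of variation (CV%) of antibody titers (for samples confirmed positive) will be provided by visit and time point". It names no geometric mean, log transformation, median or quartile for titers. For drug concentrations the same section gives a much longer list (n, mean, SD, CV%, minimum, quartiles, median, maximum), with "coefficient of variation (CV)% calculated as" 100% times SD over mean.

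SAP 8.1 has a general rule: "Continuous variables will be summarized using the number of observations (n), mean, standard deviation (SD), median, minimum, and maximum". SAP 11 does not say whether its two titer statistics add to that rule or replace it.

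SAP 11 also plans, in all treated subjects:
- antibody incidence by timepoint, which for anti-PEG includes new positivity and titer-increase categories;
- Kaplan-Meier time to positivity for each antibody;
- pegloticase concentration by antibody status.

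The protocol explains why titer size is of interest. From the earlier trials, section 7.1.2 reports: "Only 2% of subjects with anti-pegloticase antibody titers exceeding 1:2430 maintained a urate-lowering response to pegloticase", compared with 63% of those treated for at least 2 months who did not develop high titers. On infusion reactions (IRs), where the rates were 60% in the high-titer group and 19% in the other, it adds: "The incidence of IRs was higher among subjects who developed high-titer antibodies compared with those who had titers that did not exceed 1:2430". Section 9.2 gives the reason to expect a difference in transplant recipients: "immunosuppressive agents to prevent rejections have the potential to thwart the formation of ADA against pegloticase".

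**The concern.** Titers come from dilution series, so neighbouring values differ by a factor and not by a fixed amount. An arithmetic mean of such values is pulled toward the largest. With only a handful of positive samples it may describe one subject, and a CV near 200% tells the reader little more than that one value is far from the rest.

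The protocol links loss of response and infusion reactions to high titers, not to positivity as such. The mean and CV% are the only titer-size statistics that SAP 11 names. A reader comparing visits could take one subject's high titer for a general rise, or miss a modest shift in the others. The set of positive samples also changes from visit to visit, so visit means are not directly comparable unless the number positive stands beside them.

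**Working it through.** The plan gives no figure for titers and the documents contain no titer data, so there is nothing to reproduce. The check asks how the named statistics behave at the sample sizes to be expected.

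**Inputs from the documents**
- Planned size: "A sample size of 20 subjects is planned for this study" (Protocol 9.6.9).
- Antibody rates in an earlier study described in Protocol 7.1.2: 1 of 7 kidney transplant recipients, and 9 of 20 pegloticase-naive subjects without transplant or immunosuppression.
- CV% = 100 × SD / mean (SAP 11, given for concentrations).

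**Assumptions**
- Threefold dilution steps. The cut of 2430 equals 10 × 3^5, which fits, but the step is not stated.
- The two earlier rates bracket the number positive at a visit. The earlier study used a different dosing interval and at most 5 infusions, and positivity before treatment could raise the count.

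**Step 1: how many positives.** 20 × 1/7 = 2.9 and 20 × 9/20 = 9, so about 3 to 9. The estimate is loose: the exact 95% CI for 1/7 runs from 0.4% to 57.9%, or 0.1 to 11.6 subjects of 20. At a rate of 1/7, the chance of no positive or only one is (6/7)^20 + 20 × (1/7) × (6/7)^19 = 0.046 + 0.153 = 0.199. In about one case in five, then, no CV% could be computed.

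**Step 2: a worked example.** Five illustrative positives: 90, 90, 270, 270, 7290.
- Arithmetic mean = 8010 / 5 = 1602. SD = 3181. CV = 100 × 3181 / 1602 = 199%.
- As powers of three times 10, the exponents are 2, 2, 3, 3, 6, with mean 3.2 and SD 1.64. Geometric mean = 10 × 3^3.2 = 336. Geometric SD = 3^1.64 = 6.1. Median = 270.
- The top titer supplies 7290 / 8010 = 91% of the sum, and the other four samples all lie below the mean.
- Without the top titer, the arithmetic mean falls to 720 / 4 = 180 (8.9-fold) and the geometric mean to 10 × 3^2.5 = 156 (2.2-fold).
- The 95% CI for the geometric mean is 10 × 3^(3.2 ± 2.776 × 1.643 / √5) = 10 × 3^(3.2 ± 2.04), or about 36 to 3160. It is wide, as it should be with five values.

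**Step 3: dependence on spread.** Take one high titer among n − 1 equal low ones.

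| Low titer | High titer | n | Share of sum from the high titer | CV% |
|---|---|---|---|---|
| 270 | 21870 | 3 | 98% | 167 |
| 270 | 7290 | 6 | 84% | 199 |
| 270 | 2430 | 9 | 53% | 141 |
| 810 | 2430 | 3 | 60% | 69 |
| 810 | 2430 | 9 | 27% | 55 |

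In the last two rows, with titers one step apart, the arithmetic and geometric means are close: 1350 against 1168 for n = 3, and 990 against 915 for n = 9.

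**Step 4: simulation.** Exponents were drawn from a normal distribution and rounded to whole threefold steps.
- SD of 2 steps: the top titer exceeds half the sum in 80%, 71% and 59% of samples for n = 3, 5 and 9. The median ratio of arithmetic to geometric mean is 2.4 for n = 3 and above 4 for n = 9.
- SD of 0.5 step: the percentages are 39%, 7% and at most 1%, and the ratio is 1.1 to 1.2.

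Dominance by one sample is therefore a real possibility that depends on spread and on the number positive.

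**The case against.** The strongest reply is that the study's immunogenicity question is about antibody formation, and SAP 11 answers it with counts, percentages and time to positivity in all treated subjects. That stands. A reader might infer that immunogenicity as a whole is poorly answered, and the documents do not support this. Only the summary of titer size is weak. The other analyses do not fully replace it: they rest mainly on positive or negative status, the anti-PEG increase category states no size of increase, and anti-uricase has no such category.

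Second, SAP 8.1 arguably already supplies median, minimum and maximum, and subject data are listed, so an extreme titer would be visible. This is partly right. But SAP 11 spells out the full list for concentrations and only two statistics for titers, so a programmer could fairly produce just those two.

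Third, any example can be made dramatic. The set 30, 90, 90, 270, 810, 2430, 65610 has mean 9904 and geometric mean 506, a ratio of about 20. With 7290 as the top value the figures are 1573 and 370, a ratio of 4.3. This also stands: no single ratio should be quoted as the size of the problem.

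Fourth, a reader might infer that no analysis uses a high-titer cut. That cannot be established, because SAP 10.4 and Protocol 9.6.5.2 are redacted. The 1:2430 cut was also for anti-pegloticase antibodies in the earlier trials, whereas this study measures anti-PEG and anti-uricase separately.

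Finally, restricting titers to confirmed positives is not an error in itself, provided that the number positive and the number tested are shown beside them.

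**Conclusion.** The point holds as a minor one. The mean and CV% that SAP 11 names for titers, arithmetic by inference and not by statement, suit dilution-scale data poorly when few samples are positive. If titers lie several steps apart, one sample can supply most of the sum and lift the mean several-fold above the geometric mean. If they lie within about one step, little changes.

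This rests on two assumptions that the documents do not settle: the dilution step and spread of titers, and about 3 to 9 positives of 20. The endpoint is descriptive and listed under exploratory objectives. The primary analysis, the sample size and the planned incidence and time-to-positivity results are unaffected. The lack of a high-titer count is a gap in the readable text only.

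**What to change.** In SAP 11, replace the titer sentence so that, for each antibody and visit, the table shows:
- number positive over number tested;
- geometric mean titer with a 95% CI computed on the log scale, when enough samples are positive;
- median and range;
- individual titers when few samples are positive, with the number that triggers this stated in advance.

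If the redacted sections do not already contain it, add the number and percentage of ITT subjects with any titer above a pre-stated high-titer cut, for each antibody. Use 1:2430 only if the assay is shown to be comparable with the earlier one. Otherwise state another cut and its basis before the titers are seen.

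The cost is a few lines of SAP wording and minor programming. No new samples or visits are needed.

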## 12. Safety

Safety analyses will be based on the safety population.

Safety will be assessed via AEs including AEs of special interest (i.e., IRs, anaphylaxis, gout flares, and cardiovascular events), concomitant medication use (refer to [Section 9.4](#)), physical examinations, vital signs, clinical safety laboratory evaluations (complete blood count, chemistry, urine albumin:creatinine ratio), pregnancy testing (if applicable), electrocardiograms (ECGs), and biopsy confirmed renal rejection.

All safety information will be provided in subject listings.

### 12.1 Extent of Exposure

Study drug exposure will be summarized using the duration of treatment (in days), number of doses, and total dosage received for pegloticase. Interruptions in pegloticase infusions will be summarized. Reasons for infusion interruptions will be provided in the listings.

For the Pegloticase Treatment Period, the following will be summarized:

- Pegloticase
  - Number of pegloticase infusions received overall (summarized with frequency summary along with descriptive statistics of mean, SD, median, minimum, and maximum)
  - Duration in days between first and last pegloticase infusion, defined as last infusion date – first infusion date + 1 (summarized with descriptive statistics of mean, SD, median, minimum and maximum)
  - Number of incomplete infusions received (summarized with frequency summary along with descriptive statistics of mean, SD, median, minimum and maximum)
  - Number of interrupted infusions (summarized with frequency summary along with descriptive statistics of mean, SD, median, minimum and maximum)
- At each scheduled Pegloticase infusion visit
  - Number of subjects receiving a complete infusion (i.e. full dose administered)
  - Number of infusions administered without interruption
  - Number of subjects with an interrupted infusion

The usage of prophylaxis treatments (IR prophylaxis usage of fexofenadine in the evening prior to pegloticase infusion, IR prophylaxis of fexofenadine, acetaminophen, and methylpredisone on the morning prior to pegloticase infusion) will be provided in listings only.

### 12.2 Treatment Compliance

Other than the summarizations of pegloticase infusions described in [Section 12.1](#), the compliance with pegloticase will not be summarized.

### 12.3 Adverse Events

All adverse events will be coded using MedDRA version 20.1. AE monitoring will begin from the signature of the Informed Consent Form (ICF) until the 3 month Post Treatment Follow-up Visit. SAE monitoring will begin from the signature of the ICF until the 3 month Post Treatment Follow-up Visit.

#### 12.3.1 Definition of Period of Onset

- Non-treatment-emergent events:

This document is confidential.

- Adverse events with an onset date and time strictly prior to the first pegloticase treatment.
- Treatment-emergent adverse events (TEAEs):
  - Adverse events that occur on or after the start date and time of the first pegloticase infusion through 30 days after the last dose of pegloticase.
- Adverse events in the follow-up period:
  - Adverse events with an onset date more than 30 days after the last dose of pegloticase.

Missing data conventions for AEs are described in [Section 8.3.2](#). The imputed onset dates will be used to determine the period of onset.

### 12.3.2. Presentation of Results

All AEs, both serious and non-serious, will be assessed for severity using the Rheumatology Common Toxicity Criteria (CTC) v2.0. Summaries of TEAEs will be for the safety population.

An overall summary of TEAEs will be provided, including the number and percentage of subjects with each AE type as well as the number of events for each of the following:

- TEAEs
- Serious TEAEs
- TEAEs related to pegloticase
- Serious TEAEs related to pegloticase
- TEAEs with a Rheumatology CTC Criteria of 3 or higher
- TEAEs leading to permanent withdrawal of pegloticase
- TEAEs related to pegloticase leading to permanent withdrawal of pegloticase
- TEAEs leading to death
- TEAEs of special interest

Using the safety population, an overall summary of AEs occurring during the follow-up period (with onset more than 30 days after the last dose of study medication), including the number and percentage of subjects with each AE type as well as the number of events for each of the following:

- AEs
- Serious AEs
- AEs with a Rheumatology CTC Criteria of 3 or higher
- AEs leading to death
- AEs of special interest

This document is confidential.

Percentages for the overall summary of AEs during follow-up will be based on the number of subjects who had follow-up more than 30 days after last dose of medication.

Additional AE summaries will be provided by onset period, including the number, percentage of subjects, experiencing TEAEs for the following:

- TEAEs overall and by SOC and PT for the: Pegloticase Treatment Period and Follow-up Period
- TEAEs by maximum severity, overall and by SOC and PT for the Pegloticase Treatment Period
- TEAEs related to pegloticase overall and by SOC and PT for the Pegloticase Treatment Period
- TEAEs related to pegloticase by maximum severity, overall and by SOC and PT for the Pegloticase Treatment Period
- Serious TEAEs, overall and by SOC and PT for the: Pegloticase Treatment Period and Follow-up Period
- TEAEs leading to permanent withdrawal of pegloticase, overall and by SOC and PT for the Pegloticase Treatment Period

The incidence per person years of exposure to pegloticase will be provided on all tables except those summarizing events by maximum intensity, and those for the post-treatment follow-up period.

Person years of exposure to pegloticase is defined as  $[(\text{last treatment date in the period} - \text{first treatment date in the period} + 1)/365.25]$ .

For summaries by SOC, PT, and maximum severity, a subject will only be counted once for each SOC based on the maximum intensity level reported for that SOC and once for each unique PT within that SOC level at the maximum intensity level reported for that PT. For summaries by SOC and PT only, a subject will be counted at most once at the SOC level and at most once at each unique PT within the SOC level. Summaries presenting the frequency of TEAEs by SOC and PT will be ordered alphabetically by SOC and then, within a SOC, alphabetically by PT.

In addition to the listing of all AEs, separate listings will be provided for serious AEs, AEs leading to withdrawal of pegloticase, AEs leading to study discontinuation, AEs of special interest, and AEs leading to death. TEAEs and the period of onset will be identified on each listing. A listing of any subject with an interruption in treatment of pegloticase due to COVID-19 will be created which will identify AEs as pre-interruption, during interruption, or post-interruption.

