#### **Duration of Treatment and Follow-up:**

**Screening:** Up to 35 days prior to the Day 1 visit

**Treatment Period:** Pegloticase for 24 weeks (infusion visits every 2 weeks from Day 1 until the Week 22 Visit).

**End-of-Pegloticase-Infusion Visit (if applicable):** If the subject discontinues pegloticase treatment prior to the Week 22 infusion, such as due to the sUA stopping rules, the subject will complete this visit within approximately 2 weeks of the last infusion. Subjects will continue in the study.

**End-of-Study/Early Termination Visit:** Subjects who discontinue treatment during the 24-week treatment period study will be encouraged to continue study participation through the Week 24/End-of-Study Visit. Subjects who discontinue treatment prior to the Week 24 Visit and are not willing to continue in the study will complete the Early Termination Visit.

**Safety Follow-up Visit:** All subjects will receive a safety follow-up phone call/email approximately 30 days after the last dose of pegloticase to assess if any AEs/SAEs have occurred and will return to the clinic for a follow up visit 3 months after the last pegloticase infusion.

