##### **9.3.3.1.1 Study considerations for subjects ending pegloticase infusions prior to 24 weeks**

- All subjects will remain on study through Week 24 regardless of whether they stop infusions due to sUA stopping rules or other reason (e.g., withdrawal of consent for pegloticase infusions).
- Subjects are encouraged to continue to participate in all visits through the end of the study. Subjects are especially encouraged to complete study visits at the study site during key efficacy and safety collections at Weeks 20, 21, 22, 23, and 24 so that sUA labs and other key assessments can be completed. During visits between these key efficacy and safety collection visits, in subjects who have stopped infusions, subjects may complete study visits

in person or via telephone to collect AEs, concomitant medications and gout flare information.

- Activities related to pre/post infusion monitoring or medication dispensation will not be completed once a subject has stopped pegloticase infusions. These activities include:
  - Infusion reaction prophylaxis;
  - IR prophylaxis compliance;
  - Pegloticase infusion; and
  - Pegloticase PK sampling
- Re-introduction of oral ULTs should not start until after the End of Pegloticase Visit laboratory tests are collected.

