### 9.4 Treatments

#### 9.4.1 Treatments Administered

Starting at the Day 1 visit, subjects will receive pegloticase at a dose of 8 mg administered IV every 2 weeks for a total of 12 infusions from Day 1 through the Week 22 Visit.

After the Week 24 Visit, subjects should resume regular care for gout per the judgment of the treating physician, including resumption of ULT upon pegloticase discontinuation, if appropriate. Subjects will have a 3-month Follow-up visit to assess clinical status, including sUA levels.

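### SAP 12.3.2 reports follow-up AEs as a crude percentage with no follow-up-time rate, so the figure mixes AE risk with length of follow-up, which tends to be longer in early stoppers who stay on study

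*SAP*

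**What the plan says.** SAP 12.3.1 defines the follow-up AE period from each subject's own last infusion: "Adverse events with an onset date more than 30 days after the last dose of pegloticase". SAP 12.3 sets the end of collection: "AE monitoring will begin from the signature of the Informed Consent Form (ICF) until the 3 month Post Treatment Follow-up Visit". For the overall follow-up summary, SAP 12.3.2 fixes the denominator: "Percentages for the overall summary of AEs during follow-up will be based on the number of subjects who had follow-up more than 30 days" after the last dose. The same section gives incidence per person-year of pegloticase exposure "on all tables except those summarizing events by maximum intensity, and those for the post-treatment follow-up period". No rate based on follow-up time is defined in its place.

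On how long subjects are observed:

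- A completer is dosed "every 2 weeks for a total of 12 infusions from Day 1 through the Week 22 Visit" (Protocol 9.4.1).
- For early stoppers, Protocol 9.3.3.1.1 says "All subjects will remain on study through Week 24 regardless of whether they stop infusions due to sUA stopping rules or other reason". Protocol 2.1 schedules AE assessment at every visit. Protocol 9.3.3.1.1 and 9.5.7.3 allow telephone visits for stopped subjects that still collect AEs, and 9.5.7.4 includes an AE inquiry at Week 24.
- The 3-month visit is timed inconsistently. The Synopsis (Duration of Treatment and Follow-up) has a "follow up visit 3 months after the last pegloticase infusion". The Synopsis schematic, Protocol 2.1 footnote 4 and the matching SAP schedule footnote count from the End-of-Pegloticase-Infusions Visit or the Week 24/Early Termination Visit. Those two footnotes, the post-treatment text under Protocol 9.3.3.1.1, and 9.5.7.6 add that a visit falling before Week 24 will be moved, without giving a target day.

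**The concern.** The clock for follow-up AEs starts 30 days after the last dose, whenever that was. A subject who stops at Week 2 and keeps attending enters the follow-up AE table while still on the treatment-period visit schedule, and can accumulate far more time in it than a completer. The percentage counts both as one subject each. Two cohorts with the same AE rate but different proportions stopping early would then show different follow-up percentages.

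This affects the summary meant to describe safety after treatment, which includes serious AEs, deaths and AEs of special interest. Safety 3 months after treatment is an exploratory objective (Protocol 8, SAP 3.3). Elsewhere the SAP does allow for unequal time: person-years of exposure for treatment-emergent events, and month-specific denominators for gout flares (12.3.3.3).

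**Working it through.** The documents give no days-at-risk figure for the follow-up period, so there is none to reproduce.

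**Inputs**

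- Target days from SAP 8.4, Table 1: Week 2 = Day 15, Week 22 = Day 155, Week 24 = Day 169.
- Earliest last dose under the sUA stopping rule: Day 15. Week 2 and Week 4 pre-dose values are both above 6 mg/dL, and after a high Week 2 value the local Week 4 result is required before infusion (Protocol 9.5.7.2.3).
- Assumption: 3 months = 91 days. Using 90 or 92 shifts any result containing the 3 months by one day.

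**Days at risk** = (day AE collection ends) − (last dose day + 30)

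| Subject | AE collection ends | Days at risk |
|---|---|---|
| Completer, last dose Day 155 | last infusion + 91 = Day 246 | 246 − 185 = 61 |
| Completer, last dose Day 155 | Week 24 + 91 = Day 260 | 260 − 185 = 75 |
| Last dose Day 15, stays on study | Week 24 = Day 169 | 169 − 45 = 124 |
| Last dose Day 15, stays on study | Week 24 + 91 = Day 260 | 260 − 45 = 215 |
| Last dose Day 71 (Week 10), stays on study | Week 24 = Day 169 | 169 − 101 = 68 |

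Like for like, the contrast is 124/61 = 2.0-fold or 215/75 = 2.9-fold for the earliest sUA-rule stopper. It vanishes for some later stoppers: 68 days lies within the completer range.

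**Effect on the percentage.** Assume the same constant rate of 2 events per person-year in everyone and place every early stopper at Day 15. Then P(at least one AE) = 1 − exp(−2 × days/365.25):

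- 61 days: 28.4%; 124 days: 49.3%
- 75 days: 33.7%; 215 days: 69.2%

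Take two mixes of 20 subjects: 14 completers and 6 early stoppers, and 9 and 11. They stand in for the 14/20 threshold and the 43.5% Phase 3 rate in Protocol 9.6.9 (0.435 × 20 = 8.7).

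- 61 and 124 days: (14 × 0.284 + 6 × 0.493)/20 = 35%; (9 × 0.284 + 11 × 0.493)/20 = 40%.
- 75 and 215 days: (14 × 0.337 + 6 × 0.692)/20 = 44%; (9 × 0.337 + 11 × 0.692)/20 = 53%.

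At other assumed rates, with 75 and 215 days, the same change of mix gives 14.5% to 18.4% (0.5 per person-year), 26.3% to 32.8% (1) and 66.4% to 75.0% (4).

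**Event rate as a check.** With 75 and 215 days, person-time is 14 × 75 + 6 × 215 = 2,340 days (6.41 years) or 9 × 75 + 11 × 215 = 3,040 days (8.32 years). Expected events are 12.8 and 16.6; both divide back to 2 per person-year.

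**The case against.** Several counter-arguments have force.

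- **The 215 days depends on one reading.** It needs the 3-month visit to be counted from Week 24. If AE collection ended 3 months after the last infusion or after the End-of-Pegloticase-Infusions Visit, a Day 15 stopper would have 61 or 75 days, like a completer. That would close collection at Day 106 or Day 120 (15 + 91, or 29 + 91), against the AE assessments scheduled to Week 24. So 124 days is the floor for such a subject who follows the schedule; 215 is conditional.
- **The percentage also responds to risk.** A reader might infer that it tracks treatment failure instead of risk. It does not: with 6 early stoppers of 20 at 215 days, assumed rates of 0.5, 1 and 2 per person-year give 14.5%, 26.3% and 44.3%. The direction of the distortion is not assured either, because a stopper who leaves the study may add little time or drop out of the denominator.
- **Leaving out exposure-based person-years is not a mistake.** A reader might take that exclusion as the error. Exposure runs from first to last infusion and would be the wrong denominator for later events. The gap is that nothing based on follow-up time replaces it.
- **The stakes are modest.** The objective is exploratory, the study is descriptive with no formal testing (Protocol 9.6.5), and no comparison of follow-up AEs with another study is planned. Event counts accompany the percentages, SAP 9.1 reports numbers with 30 days and 3 months of follow-up, and all AEs are listed with period of onset. These help, but they supply no person-time and do not separate completers from early stoppers.
- **A rate has its own assumption.** It removes the dependence on window length only if the hazard is roughly constant, and early stoppers may resume urate-lowering therapy in this period (Protocol 9.1).

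**Conclusion.** The point holds in a limited form. The planned follow-up percentage combines AE risk with length of follow-up, and follow-up tends to be longer in early stoppers who stay on study: about 124 to 215 days for a last dose on Day 15, against about 61 to 75 for completers. The illustrated shifts, 35% to 40% and 44% to 53%, equal about one and just under two subjects in 20. They rest on an assumed constant rate of 2 per person-year and on every early stopper having the earliest last dose under the sUA rule, so real differences would probably be smaller. The documents do not support treating 215 days as established, or saying that the figure reflects failure and not risk. The primary endpoint is unaffected. This is an inexpensive improvement to a descriptive safety table.

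**What to change.** In SAP 12.3.2, add to the follow-up AE tables the number of events, and of subjects with an event, per person-year of follow-up. Count follow-up from day 31 after the last dose to the last AE contact. Show N and person-years separately for subjects who received all 12 infusions and for early stoppers, and keep the crude percentage beside them. For the subject-based rate, state whether time stops at the first event; the event rate is the one that does not depend on window length under a constant hazard.

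Also reconcile the passages on the timing of the 3-month visit: the Synopsis (duration text and schematic), Protocol 2.1 footnote 4 and its SAP counterpart, the text under Protocol 9.3.3.1.1, and 9.5.7.6. They should state when AE collection ends for a subject who stops early and stays on study.

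The cost is SAP wording, one derived follow-up-time variable and some extra columns; no new data are needed. With about 20 subjects the rates will be imprecise, and they assume a roughly constant hazard, which the SAP should say.
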